2.5.2. Background Characteristics

The following background characteristics summaries apply to Part A, Part B, and Part C, unless otherwise specified.

2.5.2.1. Participant Disposition

The number of participants in the following categories will be summarized based on participants screened:

- Number of participants screened
- Number and percentage of screen failure participants and the reason for screen failure

The percentage of participants who screen failed will be based on the number of participants screened. The percentage of participants reporting each reason for screen failure will be based on the number of participants who screen failed. A separate listing will be provided for screen failure participants with reasons for screen failure. Participants who were randomized and with any inclusion and exclusion criteria violation will also be provided in a listing.

The number and percentage of participants in each of the following disposition categories will be summarized by vaccination group based on Randomization Set, Safety Set, Immunogenicity Set, and PP Immunogenicity Set.

- Received injection
- Completed the study

• Prematurely discontinued the study and the reason for discontinuation

A participant disposition listing will be provided, including informed consent, participants who completed the study injection schedule, participants who completed study, participants who discontinued from participation in the study, with reasons for discontinuation.

The number and percentage of participants in the following categories (analysis sets defined in Section 2.4) will be summarized as defined in Section 2.5.1 (for general consideration) based on the

Randomization Set:

- Randomization Set
- Full Analysis Set
- Immunogenicity Set
- PP Immunogenicity Set
- Safety Set
- Solicited Safety Set

The denominators of the percentages will be based on participants in the Randomization Set, unless otherwise specified.

A summary table will be generated for randomized participants by site for each vaccination group and overall. A separate summary table will include the number and percentage of randomized participants by stratification factors as randomized via IRT and actual stratification factors derived from eCRF for each vaccination group and overall. Additionally, a comparison table between IRT randomization stratum and eCRF derived stratum will be provided.

2.5.2.2. Demographics and Baseline Characteristics

Descriptive statistics will be calculated for the following continuous demographic and baseline characteristics:

- Age
- Weight (kg)
- Height (cm)
- BMI (kg/m^2)

The number and percentage of participants will be provided for the following categorical variables:

- Age group 1 (18 to <50 years old, ≥ 50 to <65 years old, or ≥ 65 years old)
- Age group 2 (18 to <50 years old, ≥50 to <65 years old, ≥65 to <75 years old, or ≥75 years old)
- Sex (Male, Female)
- Race (White, Black or African American, Asian, American Indian or Alaska Native, Native Hawaiian or Other Pacific Islander, Other, Unknown, Not reported)
- Ethnicity (Hispanic or Latino, Not Hispanic or Latino, Not Reported, Unknown)
- Previous Year's Flu Vaccine Status (Received/Not received any seasonal flu vaccine anytime in the past 5 to 12 months)

The summaries will be provided separately for all analysis sets (except Solicited Safety Set) defined in Section 2.4.

2.5.2.3. Medical History

Medical history data will be coded by SOC and PT using the MedDRA version 25.0.

The number and percentage of participants with any medical history will be summarized by SOC and PT for Safety Set. A participant will be counted only once for multiple events within each SOC and PT. SOC will be displayed in an internationally agreed order. PT will be displayed in descending order of frequency of mRNA-1010 vaccination group and then alphabetically within each SOC. All the medical history data will be presented in a listing.

2.5.2.4. Prior and Concomitant Medications and Vaccinations

Prior and concomitant medications and non-study vaccinations will be coded using the WHODD, version Mar 2022. Imputation rules for missing dates of medications and non-study vaccinations are detailed in Section 7.4. The summary of concomitant medications will be based on the Safety Set.

Categorization of prior and concomitant medications are summarized in The following applies to Part A, Part B, and Part C:

Table 13 in Section 7.5. The following applies to Part A, Part B, and Part C.

An overall summary of medications and non-study vaccinations including the number and percentage of participants who take the following will be presented by vaccination group:

- Any concomitant medications and non-study vaccinations up to 28 days post-injection
- Non-study seasonal influenza vaccine up to 28 days post-injection
- Systemic steroids (≥ 10 mg/day prednisone or equivalent), immunosuppressants, immune-modifying drugs, immunoglobulins, and/or blood products administered at any time up to 28 days post-injection

The number and percentages of participants with at least one concomitant medication will be summarized by PT and vaccination group. Prior, concomitant medications, and non-study vaccination will be presented in a listing. Medications taken to prevent or treat pain or fever will also be presented in a listing. Concomitant procedures will be presented in a listing.

2.5.2.5. Protocol Deviations

The study protocol deviations will be reviewed on a regular basis and categorized in "Significant" and "Non-significant" based on the impacts on study results. Significant protocol deviations are a subset of protocol deviations that may significantly impact the completeness, accuracy, or reliability of the study data or that may significantly affect a participant's rights, safety, or well-being. Significant protocol deviations rules will be developed and finalized before database lock.

The number and percentage of the participants with each significant protocol deviation type will be summarized by vaccination group and Overall based on the Randomization Set.

Significant protocol deviations that impact critical or key study data will be determined and documented by Sponsor prior to database lock and unblinding. Participants with such significant protocol deviations will be excluded from the PP Immunogenicity Set. Reasons of exclusion from PP Immunogenicity Set will be summarized.

Significant protocol deviations will be summarized in a table and presented in a listing.

2.5.2.6. Study Exposures

The number and percentage of participants received vaccine injection at Day 1 visit, study duration \geq 7 days after vaccine injection, study duration \geq 28 days after vaccine injection as well as the study duration from vaccine injection to the EoS will be summarized by vaccination group and Overall for Safety Set. Study vaccine administration data will be presented in a listing. Participants who had dosing errors will be presented in a separate listing.

2.5.3. Immunogenicity Analysis

For immunogenicity analysis, antibody titers reported as below the LLOQ will be replaced by 0.5 x LLOQ. Values that are greater than the ULOQ will be converted to the ULOQ.

The primary analysis population for immunogenicity will be the PP Immunogenicity Set, unless otherwise specified. The primary objective of this study is to use the immunogenicity response to infer efficacy in participants receiving mRNA-1010, see Section 2.3.2 for statistical hypotheses.

Immune responses, as measured by GMT and seroconversion rate in the mRNA-1010 group based on Day 29 HAI titers, will be compared to that in participants receiving the active comparator for all 4 strains.

Rate of seroconversion is defined as the proportion of participants with either a pre-vaccination HAI titer <1:10 and a post-vaccination titer \geq 1:40 or a pre-vaccination HAI titer \geq 1:10 and a minimum 4-fold rise in post-vaccination HAI antibody titer.

The primary immunogenicity estimands are presented in detail in Table 17. The Day 29 primary analysis of immunogenicity will be performed after all participants have completed the Day 29 visit.

2.5.3.1. Analysis of Primary Endpoints

 GMT as measured by HAI against 4 vaccine-matched influenza virus A and B strains at Day 29

The GMT will be calculated using the following formula:

$$GMT = 2^{\left\{\frac{\sum_{i=1}^{n} \log_2(t_i)}{n}\right\}}$$

where, for n participants, t_i is the immunogenicity titer measurement for participant i.

An ANCOVA model will be carried out. The model will include the log-transformed HAI titers at Day 29 as the dependent variable, treatment group as the fixed variable, log-transformed baseline HAI titers as a fixed covariate, adjusting for the stratification factors. The GLSM and its corresponding 95% CI results in log-transformed scale estimated from the model will be back-transformed to obtain these estimates in the original scale, as an estimate of the GMT.

The GMR for mRNA-1010 vs. active comparator, estimated by the ratio of GLSM and the corresponding 2-sided 95% CI will be provided to assess the treatment difference and calculated by back-transforming of the difference estimated from the ANCOVA model. The corresponding 2-sided 95% CI of GMR will be provided to assess the difference in immune response between the mRNA-1010 group compared to the active comparator group at Day 29. For each strain, the noninferiority of GMT will be considered demonstrated if the lower bound of the 95% CI of the GMR is >0.667 based on a noninferiority margin of 1.5.

Descriptive statistics (n, median, min, max) will also be provided for the GMT of HAI titers with corresponding 95% CI at each timepoint. The 95% CIs will be calculated based on the t-distribution of the log-transformed values then back transformed to the original scale for presentation. In addition, the GMT with corresponding 95% CI will be plotted at each time point respectively.

• Proportion of participants reaching seroconversion at Day 29 as measured by HAI

The number and percentage of participants with seroconversion at Day 29 will be provided with 2-sided 95% CI using the Clopper-Pearson method. To compare the seroconversion rates between the treatment groups, the Miettinen-Nurminen's method will be used to calculate the 95% CI for the difference in seroconversion rates at Day 29. For each strain, the noninferiority of seroconversion rate will be considered demonstrated if the lower bound of the 95% CI of the seroconversion rate difference is > -10% based on a noninferiority margin of 10%.

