Subgroup analysis for the coprimary immunogenicity endpoints will be conducted as appropriate.

In addition, the GMT of HAI titers with corresponding 95% CI will be provided at each timepoint. The 95% CIs will be calculated based on the t-distribution of the log-transformed values then back-transformed to the original scale. The GMFR of HAI titers with corresponding

95% CI at each postbaseline timepoint over baseline will be provided. Descriptive summary statistics including median, minimum, and maximum will also be provided.

The number and percentage of participants with a HAI titer \geq 1:40 postvaccination will be provided with 2-sided 95% CI using the Clopper-Pearson method.

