Table 7 displays the time periods for collecting solicited ARs via eDiary (Section 3.8.3.5) and unsolicited AEs. MAAEs, SAEs, AESIs and AEs leading to discontinuation will be collected from Day 1 to Day 181 (Month 6)/EoS. All participants will provide blood samples that may be used for assessment of GMT, GMFR, and seroconversion, as measured by HAI (Table 7 and Section 3.8.8).

There may be situations in which the Investigator asks a participant to report for an unscheduled visit following the report of an AE. The eCRF should be completed for each unscheduled visit.

This is an observer-blind study (refer to Section 3.6.1 for details). The Investigator may unblind in the event of an emergency (refer to Section 3.5.2.7 for details).

An IST and CEAC will be involved (refer to Section 5.1.6 for details).

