4.3. Study Design (Part C)

4.3.1. Overall Design (Part C)

mRNA-1010-P303 Part C is a Phase 3, randomized, stratified, observer-blind, active-controlled study to evaluate the immunogenicity, reactogenicity, and safety of mRNA-1010 seasonal influenza vaccine in adults \geq 65 years old.

mRNA-1010 to be tested contains 4 mRNAs in an equivalent mRNA mass ratio that encode membrane-bound HA of the 4 different influenza strains recommended by the WHO for 2023-2024 NH cell- or recombinant-based vaccines. Fluzone HD Quadrivalent contains 4 HAs of the 4 different influenza strains recommended by the WHO for 2023-2024 NH egg-based vaccines.

Medically stable adults (see Part C Exclusion Criterion # 3), \geq 65 years old, will be screened and enrolled. A complete list of inclusion and exclusion criteria is provided in Section 4.4.

Approximately 3000 participants will be randomly assigned (see Section 4.6) to treatment in this study in a 1:1: ratio to 1 of 2 treatment groups to receive either a single dose of mRNA-1010 or a single dose of a licensed HD seasonal influenza vaccine (Fluzone HD Quadrivalent, Table 13).

Treatment	Study Intervention	mRNA/Antigen	Total Dose	Number of	
Group	Received	HA (each) (μg)	(μg)	Participants	
5	mRNA-1010	12.5 (of mRNA)	50 (of mRNA)	1500	
6	Active Comparator (Fluzone HD Quadrivalent)	60 (of protein)	240 (of protein)	1500	

Table 13:Treatment Groups and Dose Levels (Part C)

Abbreviations: HA = hemagglutinin; HD = high dose; mRNA = messenger ribonucleic acid

Table 11 displays the study SoA. Clinic/in-person visits will consist of a Screening Visit (up to 28 days before the Day 1 Visit and may be performed over multiple visits if within the 28-day screening window), a dosing visit on Day 1 (Baseline; may be on the same day as the Screening Visit), a visit on Day 29 (Month 1), and a subsequent visit on Day 181 (Month 6)/EoS (in a

subset of ~1000 participants) with up to 7 months of study participation for each participant. There will also be contacts by electronic means or telephone calls on Day 8, Day 91 (Month 3) and Day 181 (Month 6 [non-subset participants]).

All participants will provide blood samples for assessment of GMT, GMFR, and seroconversion, as measured by HAI (Table 11 and Section 4.8.2). Table 11 displays the time periods for collecting solicited ARs via eDiary (Section 4.8.3.4) and unsolicited AEs. MAAEs, SAEs, AESIs, and AEs leading to discontinuation will be collected from Day 1 to Day 181 (Month 6)/EoS.

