3.5.3.1. Analysis of Primary Endpoints

- GMT as measured by HAI against 4 vaccine-matched influenza virus A and B strains at Day 29 (noninferiority testing)
- Proportion of participants reaching seroconversion at Day 29 as measured by HAI (noninferiority testing)

See Section 2.5.3.1 for details.

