The same ANCOVA model for primary analysis will be applied. The superiority of GMT in participants who received mRNA-1010 compared to GMT in participants who received a licensed SD seasonal influenza vaccine (Fluarix Quadrivalent) for vaccine-matched influenza B strains will be demonstrated by the lower bound of the 97.5% or 98.8% CI of the GMR ruling out 1 (lower bound > 1).

• Proportion of participants reaching seroconversion at Day 29 as measured by HAI against vaccine-matched influenza virus B strains (superiority testing)

If superiority has been demonstrated based on GMT for vaccine-matched influenza B strains, the SCR of the vaccine-matched influenza B strains at Day 29 between the vaccination groups will be compared at the same α level. The Miettinen-Nurminen's method will be used to calculate the 97.5% or 98.8% CI for the difference in SCRs. The superiority of SCR will be considered demonstrated if the lower bound of the 97.5% or 98.8% CI of SCR difference is > 0.

• The proportion of participants with HAI titer \geq 1:40 at Day 29

The number and percentage of participants with a HAI titer ≥1:40 post-vaccination will be provided with 2-sided 95% CI using the Clopper-Pearson method.

• GMFR comparing Day 29 to Day 1 (Baseline) as measure by HAI

Descriptive statistics (n, median, min, max) will be provided for the GMFR of HAI titers with corresponding 95% CI at Day 29 over Day 1 (Baseline). The 95% CIs will be calculated based on the t-distribution of the log-transformed values then back transformed to the original scale for presentation. In addition, the GMFR with corresponding 95% CI will be plotted at Day 29.

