^d. The eDiary entries will be recorded at approximately 30 minutes after study intervention dosing while at the clinic with instruction provided by the clinic staff. Study participants will continue to record in the eDiary for solicited ARs each day after they leave the clinic, on the day of study intervention dosing and the subsequent 6 days following study intervention dosing.

^e. An unscheduled follow-up safety call may be triggered by the identification of a relevant safety event from an eDiary record, or other participant contact. A safety phone call may trigger an unscheduled visit.

^f. Trained clinic staff will call (or contact by electronic means) all participants to collect information relating to any MAAEs, AEs leading to discontinuation from study participation, SAEs, AESIs, information on concomitant medications associated with those events, and any nonstudy vaccinations.

mRNA-1010-P303

Statistical Analysis Plan, Version 2.0

Date Issued: 03APR2024

^g. All concomitant medications will be recorded from Day 1 through Day 29; thereafter, only concomitant medications relevant to or for the treatment of an SAE, AESI, or MAAE will be recorded through Day 181 (Month 6)/EoS.

^h. All non-study vaccinations will be recorded through 181 days after the dose of study intervention.

ⁱ. Samples for humoral immunogenicity on Day 181 (Month 6)/EoS will be collected for first 1000 participants and analyzed in a subset. Participants in the subset require a clinic visit on Day 181 (Month 6)/EoS for sample collection. All other participants will require a safety call.

mRNA-1010-P303

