^d. The eDiary entries will be recorded at approximately 30 minutes after study intervention dosing while at the clinic with instruction provided by the clinic staff. Study participants will continue to record in the eDiary for solicited ARs each day after they leave the clinic, on the day of study intervention dosing and the subsequent 6 days following study intervention dosing.

^e. An unscheduled follow-up safety call may be triggered by the identification of a relevant safety event from an eDiary record, or other participant contact. A safety phone call may trigger an unscheduled visit.

^f. Trained clinic staff will call (or contact by electronic means) all participants to collect information relating to any MAAEs, AEs leading to discontinuation from study participation, SAEs, AESIs, information on concomitant medications associated with those events, and any nonstudy vaccinations.

mRNA-1010-P303

Statistical Analysis Plan, Version 2.0

Date Issued: 03APR2024

^g. All concomitant medications will be recorded from Day 1 through Day 29; thereafter, only concomitant medications relevant to or for the treatment of an SAE, AESI, or MAAE will be recorded through Day 181 (Month 6)/EoS.

^h. All non-study vaccinations will be recorded through 181 days after the dose of study intervention.

ⁱ. Samples for humoral immunogenicity on Day 181 (Month 6)/EoS will be collected for approximately the first 1000 participants and analyzed in a subset. Participants in the subset require a clinic visit on Day 181 (Month 6)/EoS for sample collection. All other participants will require a safety call.

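### Parts B and C: Day 181 GMT rests on about the first 1000 enrolled, Day 1 and Day 29 on everyone, and neither a same-participant display nor a Day 181 HAI fold rise is planned

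*SAP*

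**What the plan says.** **Who is sampled.** Protocol 3.3.1 (Part B) states: "All participants will provide blood samples that may be used for assessment of GMT, GMFR, and seroconversion". Protocol 4.3.1 (Part C) states: "All participants will provide blood samples for assessment of GMT, GMFR, and seroconversion". The schedules of activities place those draws at Day 1 and Day 29 for everyone. Day 181 carries a footnote. For Part B it reads "Samples for humoral immunogenicity on Day 181 (Month 6)/EoS will be collected for first 1000 participants and analyzed in a subset" (SAP 7.1.2); for Part C, samples "will be collected for approximately the first 1000 participants and analyzed in a subset" (SAP 7.1.3). All other participants get a safety call.

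**What is displayed.** SAP 2.5.3.1 gives descriptive statistics for the HAI GMT at each timepoint and adds "In addition, the GMT with corresponding 95% CI will be plotted at each time point respectively". For Part B, SAP 3.5.3.1 says only "See Section 2.5.3.1 for details"; SAP 4.5.3.1 does the same for Part C. The one rule on the Day 181 population is in the Part A section, SAP 2.5.3.5. It restricts the Day 181 analysis alone and is not repeated for Part B. Part C has no exploratory immunogenicity analysis section in the SAP, although SAP 4.1.3 and 4.2.3 list Day 181 objectives and endpoints.

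**Fold rise.** Protocol 2.9.5.1, applied to Parts B and C by Protocol 3.9.5.1 and 4.9.5.1, says the GMFR of HAI titres with "95% CI at each postbaseline timepoint over baseline will be provided". SAP 3.5.3.4, to which Part C refers, summarises the HAI GMFR at Day 29 and says "In addition, the GMFR with corresponding 95% CI will be plotted at Day 29". SAP 3.5.3.5 gives Day 181 as GMT and seroconversion only. SAP Section 5 records no changes to the planned analysis.

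**The concern.** The Day 181 group is nested inside the Day 29 group, but it is picked by order of enrolment and not at random. If early enrollees have systematically higher or lower titres, the Day 181 GMT sits above or below the full-set Day 29 GMT for a reason unrelated to antibody decline. A reader who takes persistence from the two figures cannot separate the causes.

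The documents offer a mechanism by which composition could shift. Exclusion criterion 16 in Parts B and C bars anyone given a study influenza vaccine in the previous 12 months, while prior receipt through mRNA-1010-P302 is a stratification category. When a P302 participant becomes eligible therefore depends on the calendar, so the rollover share could change as enrolment proceeds. That shows it could happen, not that it did.

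What is at stake is the reading of an exploratory time course within each arm, plus any cross-visit comparison of GMR or seroconversion rate. The missing Day 181 GMFR also removes a summary, promised in the protocol, that sets each participant's Day 181 titre against that participant's own baseline.

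**Working it through.** **Inputs from the documents (SAP 3.3.3 and 4.3.3, and the schedule footnotes):** about 3000 randomised per Part; 15% excluded from the PP Immunogenicity Set; SD 1.5 on the natural-log scale; 1:1 allocation; about 1000 sampled at Day 181.

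**Assumptions (no figure in the documents):** the Day 181 subset loses the same 15% and splits evenly by arm (range shown: 375 to 500 per arm); the ratio r; equal SD at both visits; the within-person correlation ρ.

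**1. The plan's own figure.** 3000 × 0.85 = 2550, or 1275 per arm. For GMT superiority at GMR 1.2 and 2-sided alpha 0.025: SE = 1.5 × √(2/1275) = 0.0594; ln 1.2 / 0.0594 = 3.07; 3.07 − 2.24 = 0.83, which gives 79.6% power against the stated 79.5%. The N and SD are therefore the right ones to use.

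**2. Coverage.** Day 181: 1000 × 0.85 / 2 = 425 per arm. Share of the Day 29 set: f = 425/1275 = 1/3 (range 375/1275 = 29% to 500/1275 = 39%). About two thirds of the people behind the Day 29 point have no Day 181 value.

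**3. Composition term.** Let r be the Day 29 GMT of the subset divided by that of the others. Then

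ln GMT(full) = f · ln GMT(subset) + (1 − f) · ln GMT(others) = ln GMT(subset) − (1 − f) · ln r.

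The displayed ratio, Day 181 in the subset over Day 29 in the full set, equals the subset's true ratio times r^(1−f). With f = 1/3:

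| r (assumed) | r^(2/3) | Effect on the apparent decline |
|---|---|---|
| 0.67 | 0.77 | overstated |
| 0.80 | 0.86 | overstated |
| 1.00 | 1.00 | none |
| 1.25 | 1.16 | understated |

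Over the range of f, the factor for r = 0.8 runs from 0.85 to 0.87 and for r = 1.25 from 1.15 to 1.17. In SD units, exp[(2/3) × d × 1.5] gives 1.11, 1.22, 1.35 and 1.65 for differences d of 0.1, 0.2, 0.3 and 0.5 SD.

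**4. Chance alone.** If the subset behaved like a random third, its Day 29 GMT would differ from the full-set GMT with SE = 1.5 × √(1/425 − 1/1275) = 0.0594 per arm. The 95% range is exp(±1.96 × 0.0594) = 0.89 to 1.12.

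**5. Does matching improve precision?** Variance of the log Day 181/Day 29 ratio, with n = 425 and N = 1275:
- same participants: 2 × 1.5² × (1 − ρ)/n
- mixed sets: 1.5²/n + 1.5²/N − 2ρ × 1.5²/N

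| ρ (assumed) | 95% CI factor, same participants | 95% CI factor, mixed sets |
|---|---|---|
| 0.5 | 1.15 | 1.15 |
| 0.7 | 1.12 | 1.14 |
| 0.9 | 1.07 | 1.13 |

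Matching sets the composition term in step 3 to zero. The precision gain is nil at ρ = 0.5 and modest unless the correlation is high, so the chance term in step 4 is not the main argument.

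**The case against.** The strongest reply is that the SAP plans no waning analysis. The plotting sentence stands in the Part A section under a Day 29 endpoint, and in Part A everyone is sampled at Day 181. Parts B and C import that section for their Day 29 noninferiority endpoints. Part B's Day 181 GMT has its own text in SAP 3.5.3.5, with descriptive statistics and no plot. The word *respectively* may mean a separate plot per visit. All of this stands: a reader might infer that the SAP draws a single decline curve across visits, and the documents do not establish that. What remains is that full-set Day 29 and subset Day 181 GMTs will be reported for each arm with no matched counterpart.

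Second, the Day 181 objective is a comparison with the licensed vaccine in a subset. Enrolment order does not depend on treatment assignment, so that comparison stays randomised. This is correct, and the between-arm result at Day 181 should not be called biased.

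Third, the protocol's endpoint tables list GMFR for Day 29 only. The all-visits wording is in a section introduced as a summary for primary and secondary endpoints, and the SAP says it prevails over the protocol on methods. That makes the GMFR gap minor. It does not explain why SAP Section 5 omits it, since Protocol 2.9 says changes to exploratory analyses will be listed in the SAP or study report.

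Fourth, Part B keeps Day 181 seroconversion, which uses each participant's own baseline. A reader might infer that no within-person Day 181 measure is left; for Part B that is wrong. The Day 29 seroconversion rate is still full-set, so comparing the two visits meets the same mismatch.

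**Conclusion.** The point holds as a low-severity improvement to exploratory output. In Parts B and C, a within-arm change from Day 29 to Day 181 read from the planned summaries compares an early-enrolled third with the full set, and is off by about r^(2/3) if that third differs. The size depends wholly on r, which is assumed; if r is 1 there is no systematic error. The one-third share rests on 15% loss in the subset.

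It would be natural to conclude that restoring the Day 181 GMFR settles the matter. It does not: a Day 181 GMFR from the subset beside a full-set Day 29 GMFR has the same mismatch. Only showing the visits in the same participants removes it. Nor do the documents support any wider consequence: the Day 29 primary and secondary tests, their alpha and their power are untouched. The missing Day 181 GMFR is a separate, smaller inconsistency between protocol and SAP.

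**What to change.** In SAP 3.5.3.5, and in a new matching section for Part C:

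1. For any table or figure that includes Day 181, show the Day 1, Day 29 and Day 181 GMT, and the Day 29 and Day 181 GMFR, in the same participants: PP Immunogenicity Set members with a Day 181 sample. Give n at each point and add the within-person Day 181/Day 29 geometric mean ratio with its 95% CI.
2. Restore the Day 181 GMFR from Protocol 2.9.5.1, or list its removal with the reason in SAP Section 5.
3. Keep the full-set Day 29 results for the primary and secondary endpoints.

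Cost: SAP wording plus one table and one figure per Part, from samples already planned. The Day 29 values in this display will differ slightly from the primary table and need a footnote. The display also describes the early enrollees only, which its title should say.
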